Medical University of Karaganda

Study protocol

Analysis of laboratory markers for severe COVID-19
SC19MI-ARICU-1T
Version (V 1.0) from 10.03.2024

Karaganda, 2024

Page 1 out of 5

I. Purpose of the study and introduction.

1. **Purpose of the study :** to determine the level of significance of biochemical markers in severe patients with coronavirus infection COVID-19 hospitalized in the intensive care unit, to search for possible predictor markers of the course and outcome of this disease .
2. **Research objective:**
 - 2.1 To evaluate the indicators of biomarkers of the systemic inflammatory response in the systemic bloodstream in patients in serious condition with confirmed coronavirus infection. Based on the obtained critical levels of early markers studied at different times, it will be possible to predict the risks of developing an unfavorable outcome.
 - 2.2 Assess the structure of complications in the selected category of patients.
 - 2.3 Identify the presence of correlations between clinical and laboratory parameters (laboratory parameters and the degree of pulmonary infiltration , outcome and length of stay, age group, gender, presence of concomitant pathology).
 - 2.4 Determine critical levels of biomarkers to predict mortality. The resulting critical levels will be significant indicators in the dynamic assessment of the condition of patients in the ICU.

Introduction. The manifest course of COVID-19 often involves a fairly high risk of death due to the frequent development of serious complications in the form of Acute respiratory distress syndrome (ARDS), acute respiratory failure (ARF), pulmonary embolism (PE), sepsis, shock, multiple organ failure (MOF), and due to the absence at the current stage of highly proven safe methods of etiotropic therapy.

Of particular relevance in this regard was the search for reliable data that would make it possible to predict the severity and outcome, more effectively plan the management of different groups of patients, and provide the opportunity for timely response of medical personnel, and rational distribution of limited health care system resources during a pandemic.

Thus, in a study by Moon SS et al., which included 352 patients with identified new coronavirus infection, it has been shown that patients aged ≥ 70 years, patients with fever on admission and patients with malignancy or diabetes are more likely die from COVID-19 [1].

In the study by Zhou F, patients' old age and some concomitant diseases, such as hypertension and diabetes, were identified as factors contributing to severe progression [2]. A number of studies confirm that a comorbid background reliably suggests a more severe course of this pathology, however, of greater interest, in our opinion, is the search for more dynamic indicators. Jang JG, in addition to diabetes mellitus, hyperthermia $\geq 37.8^{\circ}\text{C}$, peripheral oxygen saturation $<92\%$ and creatine kinase-MB (CK-MB) level > 6.3 were proposed as independent predictors of severe course in hospitalized patients with COVID-19. [3]. In the study by Suh H.J.[4] dyspnea (60.0%) and elevated CRP levels (median 7.35 mg/dL; IQR 3.17–12.02) indicated severe clinical course and were suggested to evaluate patients with COVID-19 for initiation of oxygen therapy. In a prospective study by Rong-Hui Du, in addition to comorbidities and age (age ≥ 65 years, pre-existing concomitant cardiovascular or cerebrovascular diseases) as factors associated with death in patients with COVID-19-associated pneumonia cardiac troponin I ≥ 0.05 ng mL $^{-1}$ and CD3 + CD8 + T cells ≤ 75 cells $\cdot \mu\text{l}^{-1}$ were identified. The last two factors, in particular, were predictors of mortality in patients with COVID-19 pneumonia[5].

One of the hallmarks of SARS-CoV-2 infection is induced immune dysregulation, which often leads to a cytokine storm and the development of multiorgan dysfunction syndrome [6]. Available research allows us to judge what multiorgan failure syndrome appears the leading cause of high mortality among intensive care patients infected with COVID-19 [7]. This condition is based on an increased risk of developing disseminated intravascular coagulation (DIC) in patients with SARS-CoV-2, as indicated by clinical reports indicating frequent thrombocytopenia and increased D-dimer in infected individuals with manifest disease [8].

Abnormal coagulation in patients with COVID-19 is characterized by increased levels of fibrinogen and D-dimer in parallel with an increase in inflammatory markers. At the same time, an increase in prothrombin time and time of partial activation of thrombin, in combination with thrombocytopenia, suggests activation of the coagulation pathway with the development of consumptive coagulopathy due to an excessive inflammatory response. These processes cause microcirculatory dysfunction and the development of systemic microangiitis and extensive microthrombosis, which ultimately leads to multi-organ dysfunction syndrome (MODS) [7,8,9]. It is worth noting the difficulty of drawing up an optimal management plan for patients with such complications, the treatment of which should be carried out in an intensive care unit. It is even more difficult to timely assess the risk of developing these complications for timely transfer the patients to the department of anesthesiology, resuscitation and intensive care (ICU). Therefore, in addition to the data already accumulated to date, the authors of this work conducted a retrospective analysis to determine the clinical profile of patients with COVID-19 requiring intensive care, as well as to search for available and reliable predictors of the course and outcome of the disease for this cohort of patients.

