3. **Age**. From 18 years old without age restrictions
4. **Nationality (ethnicity)**. Those with different national and ethnic backgrounds undergoing treatment at the center.
5. **Criteria for inclusion** . Case histories of treated patients with severe cases confirmed by PCR of a nasopharyngeal smear of coronavirus infection COVID -19.
6. **Criteria for exclusion** . Pregnancy.
7. **Vulnerable groups** . No

III. Methods and procedures

1. **Methods and procedures** . The study plans to retrospectively analyze the medical records of patients who received treatment in the intensive care unit of the Regional Clinical Hospital for severe COVID19 infection. The retrospective analysis will evaluate the results of diagnostic procedures performed, including computed tomography of the chest and analysis of biochemical parameters, including procalcitonin, C-reactive protein, D- dimer and ferritin, identified as markers of the systemic inflammatory response.
2. **Data analysis and monitoring** . Statistical processing of the obtained data was carried out using statistical software jamovi (Computer Software , Version 2.3.26), MedCalc (MedCalc Software Ltd , Ostend, Belgium), Microsoft programs Office Excel , 2016. Statistical research methods include: calculation of median and mode, standard deviation. In order to determine correlations between quantitative and qualitative data at different stages of treatment, a correlation analysis was carried out (Spearman's test was used). To evaluate selected laboratory markers as predictors of outcome, the ROC analysis method was selected, followed by an assessment of the odds ratio (OR) taking into account the obtained J Youden index and the associated criterion (Associated criterion) for each of the selected markers in relation to patient outcome. It is preliminary planned to compile a contingency table in relation to laboratory parameters and outcomes (2x2).

Data storage and privacy. Confidentiality is ensured by encrypting the personal data of the subject with a digital code. Storage of information about patients is carried out in written form in the registration journal of the research topic, in electronic form on a computer in Microsoft program databases Excel and jamovi. Access to the data is available to the supervisor of the research and the main researcher, with the consent of the administration of the Regional Clinical Hospital of the city of Karaganda.

IV. Risk/benefit assessment

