1. **Degree of risk** . There are no risks.
2. **Potential risk** . There are no risks.
3. **Risk protection** . Each patient is assigned a code to anonymize the data.
4. **Potential benefit to the participant** . none

5. Alternatives for the participant are missing.

V. Identification of study participants, recruitment and consent

At the time of hospitalization and during treatment, informed consent was obtained from each patient for medical procedures and processing of personal data.

1. Methods for identifying participants and recruiting them . Materials (medical histories of treated patients) are selected using a continuous method in accordance with the ICU-CVI patient register for the period 08/01/2021-02/14/2022.

2. Consent process . Access to medical documentation was obtained with the consent of the administration of the Regional Clinical Hospital of Karaganda. Consent to the processing of patients' personal data was obtained during treatment in the intensive care unit of the Regional Clinical Hospital in the form of oral and written consent.

3. Participant's condition . obtaining informed consent in person from the patient/official representative.

4. Understanding . At the time of hospitalization and during treatment, informed consent was obtained from each patient for medical procedures and processing of personal data.

5. Consent forms . The informed consent form was compiled according to the recommendations of the EC.

6. Documentation of consent . Access to medical documentation was obtained with the consent of the administration of the Regional Clinical Hospital of Karaganda. Consent to the processing of patients' personal data was obtained during treatment in the intensive care unit of the Regional Clinical Hospital in the form of written consent, which is stored in the archives of the Clinic and in a scanned version in the database of an integrated medical information system.

7. Participation price . There is no cost of participation for patients.

8. Participation fee . There is no payment to the participant.

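### Objective 2.3 relates markers to length of stay without separating stays that end in death, so a single Spearman coefficient cannot by itself show a better or worse course

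*Combined protocol and SAP*

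**What the plan says.** Section I, Research objective 2.3, asks for correlations between clinical and laboratory parameters and names, among others, "outcome and length of stay, age group, gender, presence of concomitant pathology". Section III.2 (Data analysis and monitoring) uses Spearman's test for "correlations between quantitative and qualitative data at different stages of treatment" and names no other correlation method.

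Records are "selected using a continuous method in accordance with the ICU-CVI patient register" (Section V.1), and pregnancy is the only entry under "Criteria for exclusion" (Section II.6). The cohort therefore includes patients who died, as objective 2.4 also implies: "Determine critical levels of biomarkers to predict mortality".

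No section restricts stay to survivors, splits it by outcome or treats death as a competing event. None says whether stay means time in the ICU or in hospital.

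**The concern.** Length of stay has no fixed direction when patients can die. A short stay may be a quick recovery or an early death; a long stay may be a slow recovery or a late death. A Spearman coefficient over all records gives these opposite courses the same rank.

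The stated purpose is to "search for possible predictor markers of the course and outcome of this disease". If a coefficient with stay is offered as evidence about course, its sign depends on how many patients died and when, as well as on what the marker does. A harmful marker could then appear unrelated to stay, or linked to shorter stay, and be taken for a neutral or favourable sign. At stake is the length-of-stay part of objective 2.3 only.

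**Working it through.** **Plan's own figures.** There are none to reproduce. Section II.1 gives 193 records; no mortality, timing of death, stay, effect size or significance level is stated. Every other input below is an assumption.

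**What would look significant.** With n = 193 and an assumed two-sided 5% level, Fisher's approximation gives |rho| = tanh(1.96/√(193 − 3)) = tanh(0.142) = 0.14.

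**Model with fixed harm.** Marker Z ~ N(0,1). For each cause, S(t|Z) = exp[−ln 2 · (t/m)^k · HR^Z]. Discharge alive: m = 12 days, k = 1.8, HR 0.7 per SD. Death: HR 2.0 per SD. Only m and k for death vary. Rho comes from 400,000 patients per case; the percentages come from 3,000 studies of 193, with stay in whole days.

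| Death m, k | Mortality | Pooled rho | Signif. positive | Signif. negative | Discharge Cox signif. slower | Survivor-only rho |
|---|---|---|---|---|---|---|
| 90, 1.0 | 12% | +0.15 | 56% | 0% | 99% | +0.22 |
| 17, 3.0 (late) | 34% | +0.07 | 14% | 0% | 97% | +0.02 |
| 15, 1.0 (early) | 45% | -0.17 | 0% | 65% | 92% | +0.06 |
| 7, 1.2 | 65% | -0.31 | 0% | over 99% | 77% | -0.10 |

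In the same data the cause-specific Cox hazard ratios are 0.68 to 0.71 for discharge alive and 1.93 to 2.04 for death. Two further cases:

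- No effect on discharge (HR 2.0/1.0, 44% mortality): pooled rho is -0.29, significantly negative in 99% of studies. The discharge Cox model rejects in 5%.
- HR 1.5/0.5 with late deaths (34% mortality): pooled rho is +0.30, and the two methods agree in sign.

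Survivor-only rho is no benchmark either. With nobody dying it would be about +0.29, and the last column moves away from that because survivors are selected by outcome.

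**Second model, other directions.** Here logit P(death) = a + Z, with a set for 10% to 70% mortality. Log stay is log(median) + slope·Z + noise (SD 0.5 in survivors, 0.6 in deaths). The survivor median is 12 days and, in these four scenarios, the survivor slope is +0.3, giving survivor-only rho of +0.46 to +0.48.

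| Scenario: deaths' median, slope | Pooled rho, 10% to 70% mortality |
|---|---|
| A: 7 days, -0.3 | +0.30 to -0.28 (reversed) |
| C: 12 days, 0 | +0.43 to +0.17 (lowered) |
| F: 12 days, +0.3 | +0.49 to +0.45 (unchanged) |
| E: 18 days, +0.3 | +0.52 to +0.54 (inflated) |

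**Few deaths.** In a separate model (odds ratio 3 per SD for death, survivor slope +0.2, log SD 0.6), pooled rho at 5% mortality is 0.21 to 0.34 against about 0.30 in survivors.

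**Limits of the alternatives.** In scenario E the death hazard ratio is about 0.94 at 10% mortality and 0.69 at 70%, although the marker raises the odds of death by e¹ ≈ 2.7 per SD. A score with all deaths tied as worst correlates 0.42 with the marker in E and F at 70% mortality, against 0.38 for death alone.

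**The case against.** The strongest reply is that objective 2.3 promises only to look for correlations. It does not say that stay measures course, and pooled stay answers a fair question about bed use, in line with the Introduction's interest in the "rational distribution of limited health care system resources during a pandemic". That stands, and it is why the coefficient may be kept for that purpose.

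Pooling is also inferred from silence. A reader might conclude that the plan prescribes it; no section does. The wording of 2.3 could even be read as pairs, with outcome set against stay. Marker against stay is still a natural reading, and a single coefficient is what results if nothing more is specified.

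All sizes are assumed. A reader might infer that the planned coefficient will be reversed or lowered in this cohort. The documents do not support that: in the second model, reversal against a positive survivor slope needs an opposite slope in deaths, and some settings show no distortion. The point is that the plan gives no means of telling these settings apart.

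The fixed-harm model also favours Cox regression, since it generates proportional cause-specific hazards. Scenario E shows that the death hazard ratio can itself mislead, so the fix carries that warning. Finally, a reader might dismiss a deaths-as-worst score as a restatement of mortality. With deaths tied this is not generally so: in A, C, E and F at 10% mortality it gives 0.52 against 0.26 for death alone.

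**Conclusion.** The gap is real and limited. The sign and size of a Spearman coefficient between a marker and stay over all records cannot by themselves be read as a better or worse course. Under the assumed fixed-harm model, mortality and its timing alone move it from clearly positive to clearly negative, and both ends exceed the 0.14 that would look significant at n = 193. No direction or size can be claimed for this cohort.

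A reader might extend the criticism to the mortality cut-offs. That is not supported: the ROC, Youden and odds-ratio analysis uses outcome directly and does not depend on stay. Importance is minor to moderate, since this is one correlate in an exploratory objective.

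**What to change.** 1. Define stay: ICU or hospital, with its start and end.
2. For the marker-versus-stay part of objective 2.3, analyse time to discharge alive with death as a competing event. Fit cause-specific Cox models per log2 admission marker, one for discharge alive and one for death, and report them side by side.
3. State that the death hazard ratio must not be read alone, because slower discharge leaves patients at risk for longer. Conclusions on mortality stay with objective 2.4.
4. Keep the pooled Spearman coefficient as a description of bed use only, and label coefficients by outcome as descriptive.
5. A score with all deaths tied as worst is an acceptable simple sensitivity analysis.
6. Objective 2.1 refers to "critical levels of early markers studied at different times". Analyse later measurements this way only if their dates are recorded, starting the clock at measurement among patients still in the unit or hospital, according to the definition of stay.

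Cost: one definition and two one-covariate models per marker and time point, so 4 × 2 = 8 for the four named markers at admission. Outcome and stay are already needed. There is more to explain, later time points add models and have fewer patients, and the documents do not say whether measurement dates are held.

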3. **Age**. From 18 years old without age restrictions
4. **Nationality (ethnicity)**. Those with different national and ethnic backgrounds undergoing treatment at the center.
5. **Criteria for inclusion** . Case histories of treated patients with severe cases confirmed by PCR of a nasopharyngeal smear of coronavirus infection COVID -19.
6. **Criteria for exclusion** . Pregnancy.
7. **Vulnerable groups** . No

III. Methods and procedures

1. **Methods and procedures** . The study plans to retrospectively analyze the medical records of patients who received treatment in the intensive care unit of the Regional Clinical Hospital for severe COVID19 infection. The retrospective analysis will evaluate the results of diagnostic procedures performed, including computed tomography of the chest and analysis of biochemical parameters, including procalcitonin, C-reactive protein, D- dimer and ferritin, identified as markers of the systemic inflammatory response.
2. **Data analysis and monitoring** . Statistical processing of the obtained data was carried out using statistical software jamovi (Computer Software , Version 2.3.26), MedCalc (MedCalc Software Ltd , Ostend, Belgium), Microsoft programs Office Excel , 2016. Statistical research methods include: calculation of median and mode, standard deviation. In order to determine correlations between quantitative and qualitative data at different stages of treatment, a correlation analysis was carried out (Spearman's test was used). To evaluate selected laboratory markers as predictors of outcome, the ROC analysis method was selected, followed by an assessment of the odds ratio (OR) taking into account the obtained J Youden index and the associated criterion (Associated criterion) for each of the selected markers in relation to patient outcome. It is preliminary planned to compile a contingency table in relation to laboratory parameters and outcomes (2x2).

Data storage and privacy. Confidentiality is ensured by encrypting the personal data of the subject with a digital code. Storage of information about patients is carried out in written form in the registration journal of the research topic, in electronic form on a computer in Microsoft program databases Excel and jamovi. Access to the data is available to the supervisor of the research and the main researcher, with the consent of the administration of the Regional Clinical Hospital of the city of Karaganda.

IV. Risk/benefit assessment

1. **Degree of risk** . There are no risks.
2. **Potential risk** . There are no risks.
3. **Risk protection** . Each patient is assigned a code to anonymize the data.
4. **Potential benefit to the participant** . none

5. Alternatives for the participant are missing.

V. Identification of study participants, recruitment and consent

At the time of hospitalization and during treatment, informed consent was obtained from each patient for medical procedures and processing of personal data.

1. Methods for identifying participants and recruiting them . Materials (medical histories of treated patients) are selected using a continuous method in accordance with the ICU-CVI patient register for the period 08/01/2021-02/14/2022.

2. Consent process . Access to medical documentation was obtained with the consent of the administration of the Regional Clinical Hospital of Karaganda. Consent to the processing of patients' personal data was obtained during treatment in the intensive care unit of the Regional Clinical Hospital in the form of oral and written consent.

3. Participant's condition . obtaining informed consent in person from the patient/official representative.

4. Understanding . At the time of hospitalization and during treatment, informed consent was obtained from each patient for medical procedures and processing of personal data.

5. Consent forms . The informed consent form was compiled according to the recommendations of the EC.

6. Documentation of consent . Access to medical documentation was obtained with the consent of the administration of the Regional Clinical Hospital of Karaganda. Consent to the processing of patients' personal data was obtained during treatment in the intensive care unit of the Regional Clinical Hospital in the form of written consent, which is stored in the archives of the Clinic and in a scanned version in the database of an integrated medical information system.

7. Participation price . There is no cost of participation for patients.

8. Participation fee . There is no payment to the participant.

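### Does leaving the blood sample behind each ROC cut-off unnamed undermine the use of the cut-offs at different times and in dynamic assessment?

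*Combined protocol and SAP*

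**What the plan says.** The analysis text is in Section III.2 (Data analysis and monitoring). Markers are assessed as predictors of outcome by ROC analysis, followed by an odds ratio based on "the obtained J Youden index and the associated criterion (Associated criterion) for each of the selected markers in relation to patient outcome", and a 2x2 table of laboratory parameters against outcome. No sampling time is attached to these steps. Time enters Section III.2 only through the Spearman analysis of "correlations between quantitative and qualitative data at different stages of treatment", and the stages are not defined.

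The uses are in the research objectives of Section I:

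- Objective 2.1: "Based on the obtained critical levels of early markers studied at different times, it will be possible to predict the risks" of an unfavourable outcome.
- Objective 2.3 lists the correlations of interest, among them laboratory values with "outcome and length of stay, age group, gender, presence of concomitant pathology".
- Objective 2.4: "Determine critical levels of biomarkers to predict mortality", followed by "The resulting critical levels will be significant indicators in the dynamic assessment of the condition of patients in the ICU".

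After discussing comorbidity as a risk factor, the introduction adds that "of greater interest, in our opinion, is the search for more dynamic indicators".

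**The concern.** Read together, these sections suggest a mismatch. The ROC step seems to yield one cut-off per marker from one unspecified reading per patient, whereas the objectives appear to use that cut-off repeatedly during the ICU stay.

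Three consequences would follow if that reading were right.

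- A patient checked several times against the same threshold has several chances to cross it, so the single-reading specificity would overstate performance.
- A cut-off derived from the highest value of the stay would be too high for a first sample and would miss deaths early on.
- A peak tends to be higher when more samples are taken. A correlation with length of stay could then appear for a marker that has none.

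Choosing the measurement after seeing results would also be a free analytic choice. The critical levels are the main product of this study, so these points deserve a check.

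**Working it through.** **Inputs.** The protocol gives 193 records, selected consecutively from the ICU register. It gives no mortality, AUC, sensitivity, specificity, within-patient variability or sampling frequency, so there is no stated figure to reproduce. Everything below is assumed: a normally distributed marker with SD 1 in survivors and in deaths, one-sample AUC 0.65 to 0.80, within-patient correlation r of 0.5 to 0.9, and no real change over time.

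**One reading.** The separation of the groups is d = √2·Φ⁻¹(AUC). The Youden cut-off is c = d/2, and sensitivity = specificity = Φ(d/2). For AUC 0.70, d = 0.742, c = 0.371 and both are 0.645, so 35.5% of survivors lie above the cut-off.

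**Several readings, positive if any one crosses.** P(all m readings ≤ c) = ∫ φ(z)·Φ((c − μ − √r·z)/√(1 − r))^m dz, with μ = 0 for survivors and μ = d for deaths.

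| Readings | Survivors above (AUC 0.70, r 0.67) | Deaths above | Survivors above, full range | Deaths above, full range |
|---|---|---|---|---|
| 1 | 0.355 | 0.645 | 0.28–0.39 | 0.61–0.72 |
| 3 | 0.548 | 0.823 | 0.37–0.64 | 0.71–0.91 |
| 7 | 0.674 | 0.901 | 0.43–0.79 | 0.77–0.97 |

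Sensitivity rises along with false positives, so mainly the operating point moves. In the example the Youden index goes from 0.645 − 0.355 = 0.290 to 0.823 − 0.548 = 0.275 over three readings, and to 0.901 − 0.674 = 0.227 over seven.

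**Several readings, each judged alone.** Under the same model every later reading has the same distribution as the first. Sensitivity and specificity therefore stay at 0.645 at each reading. The growth in the table comes entirely from the any-crossing rule.

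**A peak instead of a first value.** Maximising the Youden index on the peak of 3 or 7 readings puts the cut-off 0.27–0.58 or 0.43–0.94 SD above the first-sample cut-off. Applied to a first sample, sensitivity then falls by 0.10–0.23 or 0.16–0.36 at the population cut-offs. Specificity rises in return. In the example, the peak of 3 gives 0.458 and 0.802, against 0.645 for both. At N = 193 the sampling SD of the difference between the two cut-offs is 0.29–0.49 SD, of the same order as the shift for a peak of 3.

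**Length of stay.** For a marker unrelated to death or stay, with the peak used and a mean of 5 samples per patient, Spearman's rho with the number of samples is 0.12–0.20 at r of 0.5 to 0.8, significant in 37–83% of simulated data sets. At r = 0.9 it is about 0.08, significant in about 21%. This takes the number of samples as a stand-in for length of stay, which the protocol does not do.

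**Against the text.**

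- The any-crossing rule appears nowhere. Objective 2.4 names dynamic assessment, and judging the current value each day fits that equally well.
- A peak value appears nowhere, and Objective 2.1 speaks of early markers, which points away from it.
- Section III.2 assigns a criterion to each marker and is silent on time. The plural critical levels in Objective 2.1 fit one cut-off per time point as well as a single one.
- The introduction's remark about dynamic indicators contrasts changeable factors with fixed comorbidity. It does not set a rule for serial use.

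**The case for a change.** The strongest case for a change is that the text is incomplete on either reading. With one cut-off per marker, the reading it describes is not identified. With one per time, the times are missing, as are the patients and deaths at each. Naming the sample would cost a line of text, and the past tense in Section III.2 suggests that some choices had already been made. Error rates also need not carry over even when each reading is judged alone. If the marker rose by 0.5 SD in both groups, the AUC 0.70 cut-off would move to sensitivity 0.81 and specificity 0.45; a fall of 0.5 SD would reverse these figures.

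The incompleteness stands: the measurement, the times and the stages are undefined, and the performance of the cut-offs in serial use is not established. What does not stand is the step from there to a faulty analysis. A drifting marker is handled by the per-time reading of Objective 2.1, because a cut-off estimated on a given day reflects that day's distribution in the patients still in the ICU. Error rates for serial use would need dated repeat samples, and no section establishes that the records hold them.

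**Conclusion.** No change to the plan follows. This is missing detail that an analyst fills sensibly: the first value after ICU admission, or one value per day with the number of patients and deaths alongside. Either choice gives a valid ROC analysis for the measurement used. If all 193 patients contribute a first value, the sampling SD of the AUC is 0.03–0.04, assuming an AUC of 0.65–0.80 and 30–60% deaths.

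The large figures are conditional. The 37–64% and 43–79% of survivors flagged over three or seven readings need an any-crossing rule. The sensitivity losses of 0.10–0.23 and 0.16–0.36, and the spurious correlation with stay, need a peak value. The protocol contains neither, and all the figures rest on assumed AUCs and correlations. The wording of Objective 2.4 goes further than the analysis, so a reader should take any reported sensitivity and specificity as applying to the sample analysed and not to serial monitoring. That limits interpretation without making the planned analysis unsound.
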